13 STATISTICAL CONSIDERATIONS

13.1 Study Design

This is a single-arm phase 2 study of sorafenib, valproic acid, and sildenafil in the treatment of patients with recurrent high-grade glioma. The primary objective is to determine the efficacy of the drug combination in terms of 6-month PFS. This study will be conducted through an adaptive design potentially including 2 Simon's two-stage mini-max designs. Initially, recurrent high-grade glioma patients will be enrolled, regardless of tumor molecular subtype, to determine the efficacy of the drug combination. If efficacy criteria are not met in patients inclusive of all molecular subtypes, then only patients with tumors that express PDGFR α will be enrolled. Therefore, 2 Simon's designs may be included; the first is for patients in the entire cohort and the second is for patients with PDGFR α expressing tumors only if efficacy criteria are not met in the entire cohort. Details on the rationale of the adaptive design can be found in Section [1.9](#).

The total expected sample size is estimated to be 44, with a range from 32 to 66 patients.

Both a safety lead-in and a safety stopping rule are provided to monitor whether there are "too many" unexpected toxicities related to the drug combination, as patients continue being enrolled in the study. To ensure safety with respect to any interaction toxicity effects among the 3 drugs, we provide a safety lead-in rule for the first 6 qualifying toxicity-evaluable patients—like a "3+3" phase 1 design. Once a dose has been identified wherein < 2 of 6 qualifying toxicity-evaluable patients develop a qualifying toxicity during the first 4 weeks of therapy, then that dose will be used for expansion. Qualifying toxicities are defined in Section [6.4.2](#).

Once the dose for expansion to the full cohort is identified, then an early sequential safety stopping rule which is based on the occurrence rate of qualifying grade 3 or greater toxicities is provided to monitor safety for any toxicities in the expansion. The safety lead-in rule is designed for a "3+3" study and is used to enhance safety analysis for the first 6 qualifying toxicity-evaluable patients on the study, whereas the sequential stopping rule for subsequent enrollment has considered the variability of toxicity rate by confidence intervals based on observed data and scenarios where unacceptable toxicity could occur prior to study suspension. More details on the clinical rationale are in Section [1.7](#). Details on the safety lead-in and safety stopping rule are in Section [13.6](#).

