13.2 Sample Size/Accrual Rates

The sample size and power are calculated based on Simon's two-stage mini-max design which minimizes the expected maximum sample size ([35](#)). The primary outcome, 6-month PFS, is considered as a binary variable, ie, a patient either has 6-month PFS or not. Per the previous studies of second-line therapy in GBM, we assume that the null hypothesis, the proportion of patients who have 6-month PFS, is $\leq 20\%$, ie, $p_0 \leq 0.2$, which is unacceptably low, and the true proportion is $p_1 = 0.4$. With a one-sided type I error of 5% and power of at least 80%, the first stage will enroll 16 response-evaluable patients. If there are 3 or less response-evaluable patients who have 6-month PFS, then the trial in the unselected patient population will end. If 4 or more response-evaluable patients have 6-month PFS, then the trial will enroll an additional 17 response-evaluable patients into the second stage. If 11 or more out of the total of 33 response-evaluable patients have 6-

month PFS, the drug combination meets efficacy criteria and further studies can be pursued.

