As mentioned in Section [13.1](#), the study will be conducted through an adaptive design possibly with 2 Simon's two-stage designs. Both of these Simon's designs will share the same parameters/settings, assumptions for sample size, and power calculations. The total sample size may range from 32 to 66. We expect that it is very likely that the study will enroll 16 response-evaluable patients inclusive of all molecular subtypes, and then a total of 16 response-evaluable patients with PDGFR α -expressing tumors in the first stage (inclusive of patients with PDGFR α -positive tumors in the first interim analysis), and an additional 17 response-evaluable patients with PDGFR α -expressing tumors in the second stage. Per previous studies, PDGFR α is the third most common gene event identified in GBM, and about 30-40% patients have positive PDGFR α expression among all GBM patients, with a higher percentage in patients with transformed GBM from lower grade glioma ([39](#)). Therefore, we expect that the total sample size for the adaptive design is about 44 response-evaluable patients. Based on previous recruitment at the Massey Cancer Center, it is estimated that 8-12 patients will be enrolled per year, and therefore, it is estimated that the study will complete enrollment in approximately 4 years and be closed in approximately 5 years. It is likely that the accrual rate for the PDGFR α expression cohort will be slower than for the entire population and the study team will invite more clinical sites to increase the accrual rate.

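### The 'expected' total of 44 is the size of one path through the adaptive design, not an average over its stopping rules, and the 32 to 66 range uses a different carry-over rule

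*Combined protocol and SAP*

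**What the plan says.** Section 13.1 gives the total as "The total expected sample size is estimated to be 44, with a range from 32 to 66 patients". Section 13.2 sets a null rate of 20% and an alternative of 40% for 6-month PFS. The error rates are given as "With a one-sided type I error of 5% and power of at least 80"%, and "the first stage will enroll 16 response-evaluable patients". The futility rule reads: "If there are 3 or less response-evaluable patients who have 6-month PFS, then the trial in the unselected patient population will end". Otherwise 17 more are enrolled, and success is 11 or more of 33. The PDGFRα design uses the same parameters.

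Section 13.2 then describes one sequence: "We expect that it is very likely that the study will enroll 16 response-evaluable patients inclusive of all molecular subtypes". The PDGFRα first stage is next completed to 16, counting positives from the first interim, and 17 more positives are added. With 30-40% of GBM patients taken as PDGFRα-positive, the section concludes: "Therefore, we expect that the total sample size for the adaptive design is about 44 response-evaluable patients".

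The documents describe the opening of the second design in two ways. Sections 1.9, 4.1.1 and 11.2 and footnote L of the Study Calendar tie the switch to the first interim analysis. Section 13.1 opens the second design if the entire cohort does not meet efficacy criteria, and its maximum of 66 (33 + 33) can be reached only if failure at 33 also opens it.

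**The concern.** An expected sample size for a design with stopping rules is an average over the ways the trial can end, under stated response rates. Sections 13.1 and 13.2 give no such average, no path probabilities and no subgroup rates. The figure of 44 presupposes two events: the unselected cohort fails its first stage, and the PDGFRα cohort passes its own. Calling that sequence very likely tells reviewers that the trial will probably reach the second stage of its PDGFRα test, the main reason for the adaptive design in Section 1.9. The enrolment and closure estimates follow directly from 44 in the text. The range in the same sentence also appears to rest on a different rule from the 44 inside it.

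**Working it through.** **Inputs.** From Section 13.2: p0 = 0.20, p1 = 0.40; boundaries 3/16 and 10/33 (stop at 3 or fewer of 16, succeed at 11 or more of 33); the same boundaries for the PDGFRα design; prevalence f = 0.30-0.40; positives already treated are carried over. *Assumed:* subgroup rates p+ and p−, and that the prevalence stated for GBM applies to all enrolled patients. All totals are response-evaluable patients.

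**1. Reproduce 44.** 16 + (16 − 16f) + 17 = 49 − 16f, which is 44.2, 43.4 and 42.6 at f = 0.30, 0.35 and 0.40. So 44 is the size of this one path.

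**2. Check the single Simon design.** Exact type I error is 0.0475 and power 0.811. The boundaries meet their stated error rates.

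**3. Bound the path probability.** The path needs 3 or fewer successes in the first 16. With X ~ Bin(16, overall rate), P(X ≤ 3) = 0.598 at 20% and 0.065 at 40%. This depends only on the overall rate, however it splits by PDGFRα status. Whenever the overall rate is 20% or more, the path therefore has probability below 60%.

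**4. Path probability.** Let K ~ Bin(16, f) be the positives among the first 16, a ~ Bin(K, p+) and b ~ Bin(16 − K, p−) the successes. The path requires a + b ≤ 3 and a + Y ≥ 4, with Y ~ Bin(16 − K, p+) among the new positives. Sum the exact probabilities over K, a and b. In scenario D, p− = (0.20 − 0.40f)/(1 − f) = 0.114, 0.092 and 0.067.

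| Scenario | Probability of the 44-patient path, f = 0.30-0.40 |
|---|---|
| A: 20% in all | 17-19% |
| B: 40% in all | 5% |
| C: 40% in positives, 20% in negatives | 26-33% |
| D: 20% overall, 40% in positives | about 54% |

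**5. Mean N and entry to PDGFRα stage 2, under each opening rule.**

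| Scenario | Opens only after the stop at 16: mean N | Stage 2 entered | Also opens after failure at 33: mean N | Stage 2 entered |
|---|---|---|---|---|
| A | 32-33 | 17-19% | 36-38 | 36-37% |
| B | 33.5 | 5% | 35-36 | 15-16% |
| C | 35-37 | 26-33% | 43-46 | 65-73% |
| D | 38-39 | about 54% | 45-47 | about 89% |

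**6. The range.** Without carry-over, the shortest path through both designs is 16 + 16 = 32 and the longest is 33 + 33 = 66, the stated limits. With the carry-over used for 44, failing both first stages gives 32 − 16f = 27.2 to 25.6 (about 25-27 when averaged over the trials that fail both). The longest path gives 66 − 33f = 56.1 to 52.8. These are averages; single trials vary with the number of positives.

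**The case against.** The strongest reply is that Section 13.2 shows the sequence openly, says about 44, and uses the number only for planning. No boundary or conduct rule depends on it. Four years at 8-12 patients per year gives 32-48, so the timeline tolerates most of the means above. This limits the consequence but does not make the label correct.

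The authors may also have expected an overall rate below 20%: Section 1.7 reports 6-month PFS of 0-26% for earlier sorafenib combinations. With 40% in positives and 0% in negatives the path does reach 69-82%. But the plan states no such assumption.

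Three stronger readings are tempting, and the documents do not support them:

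- A reader might infer that the path never exceeds about a third at the plan's rates. Scenario D uses the same 20% and 40% and gives about 54%.
- A reader might infer that 44 is wrong as a mean in every case. If failure at 33 also opens the PDGFRα design, as the maximum of 66 implies, the mean is 43-47 in scenarios C and D. The closeness is coincidental, because it averages quite different totals, but it is there.
- A reader might infer that the PDGFRα second stage is reached in at most a third of trials when only positives benefit. That holds only in scenario C and only if the design opens solely after the stop at 16; otherwise it is 65-73%.

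Harm to supply or budget planning cannot be argued either, since the visible text says nothing about them.

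**Conclusion.** Wrong as written, with modest consequences. The 44 is the total for one path and is mislabelled as an expectation. The description of that path as very likely is unsupported: its probability runs from about 5% to about 54% across the four scenarios, and cannot reach 60% while the overall rate is at or above the plan's own null. The range of 32 to 66 is inconsistent with 44 because the two treat carried-over positives differently. How far 44 lies from the true mean cannot be fixed until the opening rule is settled. It is too high in all four scenarios under the narrow rule (32-39). Under the broad rule it is too high for a uniform rate (35-38) and near the mean when positives have 40% (43-47). These results rest on assumed subgroup rates, on GBM prevalence applied to all patients, and on retaining the outcomes of carried-over positives.

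**What to change.** 1. Reconcile Sections 1.9, 4.1.1 and 11.2 and Study Calendar footnote L (switch at the first interim) with Section 13.1 and the maximum of 66 (second design also opens after failure at 33). State which opening rule applies.
2. In Sections 13.1 and 13.2, relabel the figure along these lines: *about 43-44 if the unselected cohort stops at 16 and the PDGFRα cohort enters its second stage*. Delete the statement that this sequence is very likely.
3. Recompute the range with the same carry-over rule as the 43-44.
4. Add a small table, by stated scenario and under the chosen opening rule, of mean N and the probability of entering PDGFRα stage 2. The matching columns in step 5 of the working can serve as a starting point.

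The cost is wording and one table, with no change to enrolment or conduct. The planning statement becomes less favourable.

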13.2 Sample Size/Accrual Rates

The sample size and power are calculated based on Simon's two-stage mini-max design which minimizes the expected maximum sample size ([35](#)). The primary outcome, 6-month PFS, is considered as a binary variable, ie, a patient either has 6-month PFS or not. Per the previous studies of second-line therapy in GBM, we assume that the null hypothesis, the proportion of patients who have 6-month PFS, is $\leq 20\%$, ie, $p_0 \leq 0.2$, which is unacceptably low, and the true proportion is $p_1 = 0.4$. With a one-sided type I error of 5% and power of at least 80%, the first stage will enroll 16 response-evaluable patients. If there are 3 or less response-evaluable patients who have 6-month PFS, then the trial in the unselected patient population will end. If 4 or more response-evaluable patients have 6-month PFS, then the trial will enroll an additional 17 response-evaluable patients into the second stage. If 11 or more out of the total of 33 response-evaluable patients have 6-

month PFS, the drug combination meets efficacy criteria and further studies can be pursued.

As mentioned in Section [13.1](#), the study will be conducted through an adaptive design possibly with 2 Simon's two-stage designs. Both of these Simon's designs will share the same parameters/settings, assumptions for sample size, and power calculations. The total sample size may range from 32 to 66. We expect that it is very likely that the study will enroll 16 response-evaluable patients inclusive of all molecular subtypes, and then a total of 16 response-evaluable patients with PDGFR α -expressing tumors in the first stage (inclusive of patients with PDGFR α -positive tumors in the first interim analysis), and an additional 17 response-evaluable patients with PDGFR α -expressing tumors in the second stage. Per previous studies, PDGFR α is the third most common gene event identified in GBM, and about 30-40% patients have positive PDGFR α expression among all GBM patients, with a higher percentage in patients with transformed GBM from lower grade glioma ([39](#)). Therefore, we expect that the total sample size for the adaptive design is about 44 response-evaluable patients. Based on previous recruitment at the Massey Cancer Center, it is estimated that 8-12 patients will be enrolled per year, and therefore, it is estimated that the study will complete enrollment in approximately 4 years and be closed in approximately 5 years. It is likely that the accrual rate for the PDGFR α expression cohort will be slower than for the entire population and the study team will invite more clinical sites to increase the accrual rate.

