1.9 Rationale for Adaptive Design

All patients with recurrent or progressive high-grade glioma will be eligible for the study. Sorafenib is a multikinase inhibitor, with a wide variety of cellular effects. Not enough is known about the *in vivo* mechanisms of action and resistance to the drug to justify initial exclusion of molecular subtypes of high-grade glioma. There will be an interim analysis, however; at which point the decision will be made whether or not to continue with all subtypes of high-grade glioma, based on pre-specified efficacy criteria. If efficacy criteria are not met for the combined group, the study will continue with only patients who have PDGFR α expressing tumors, since PDGFR α is a target of sorafenib and this is the most promising subgroup in preclinical models. A second interim analysis will be performed once enough patients with PDGFR α expressing tumors have been accrued, to determine if the drug combination is worth pursuing in this specific patient population.

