3 STUDY DESIGN

3.1 General Description

The study is a single-center, open-label phase 2 study, with an early stopping rule in place for safety. The trial will include patients with recurrent or progressive high-grade glioma. The trial will be conducted in an adaptive design, with a Simon's mini-max 2-stage design (35) incorporating an interim analysis for efficacy. If efficacy endpoints are not reached, the trial focus will be narrowed to include only the subgroup of patients whose tumors express PDGFR α . The trial will continue with this cohort in a second Simon's mini-max 2-stage design, with an additional interim efficacy analysis of this subgroup.

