4 PATIENT SELECTION

4.1 Inclusion Criteria

A patient must meet all of the following inclusion criteria to be eligible to participate in the study:

- 4.1.1 Pathologically confirmed high-grade glioma (WHO grade 3 or 4), with documented CT or MRI progression or recurrence. Biopsy is also an acceptable method of confirming progression. If initial tumor was grade 2 glioma, histological confirmation of high-grade recurrence is required.
- After first interim analysis, if the study proceeds to enrollment of selected patients (only those who have PDGFR α -positive tumors), patients will be pre-registered for PDGFR α analysis and registered to the combination treatment schema only if PDGFR α -positive and all other enrollment criteria are met.
- 4.1.2 Measurable or evaluable disease by RANO (MRI) or Macdonald (CT) criteria (see Section [10.2](#)).
- 4.1.3 Fixed or decreasing dose of corticosteroids (or no corticosteroids) for at least 1 week prior to cycle 1 day 1.
- 4.1.4 Age \geq 18 years.
- 4.1.5 At least 12 weeks since the completion of radiation therapy to a total of \geq 50 Gy.

4.1.6 ECOG performance status of 0, 1, or 2 ([Appendix 1](#)).

4.1.7 Clinical laboratory parameters:

- WBC $\geq 3,000/\text{mm}^3$
- ANC $\geq 1,500/\text{mm}^3$
- Platelets $\geq 100,000/\text{mm}^3$
- Hgb ≥ 8.5 g/dL
- AST, ALT ≤ 3 x upper limit of normal (ULN) for the laboratory
- Total bilirubin ≤ 1.5 x ULN for the laboratory (total bilirubin criteria may be waived if a patient has documented Gilbert's disease)
- Creatinine clearance (CrCL) ≥ 30 mL/min as calculated by the standard Cockcroft-Gault equation ([Appendix 2](#))

4.1.8 Women of childbearing potential must have a negative serum pregnancy test performed within 7 days prior to the start of treatment.

4.1.9 Women of childbearing potential and men must agree to use a medically accepted form of birth control for the duration of study participation and for 2 months following completion of study treatment.

4.1.10 Ability to understand and the willingness to sign a written informed consent document.

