11.2 Timing of Sample Collection and Analysis

In the initial PDGFR α -unselected cohort, archived samples may be obtained and submitted for initial processing any time after study consent is obtained, preferably within the first few weeks of study therapy. Analysis/interpretation of these samples may be done without regard to participant initiation of study treatment. Samples may be held for batch processing, staining, and analysis until such time as it is determined whether the study will proceed to enrollment of only patients known to have PDGFR α -positive tumors.

If the study continues to enrollment of a PDGFR α -positive cohort, archived samples will need to be collected, processed, and scored as part of the screening process to determine eligibility.

After the first interim analysis for 6-month PFS:

- If the study continues with enrollment of PDGFR α -unselected patients only, tissue collection, processing, and analysis may continue, with the understanding that samples may be processed and/or analyzed for PDGFR α status in a non-CLIA-certified setting. In

this case, samples will be deparaffinized in VCU Anatomic Pathology, immunostained in the VCU Massey Cancer Center Clinical and Translational Research Laboratory (VCU MCC CTRL) and scored in VCU Anatomic Pathology.

- If the study continues with enrollment of PDGFR α -selected patients (only those who have PDGFR α -positive tumors), results of PDGFR α immunostaining will need to be available PRIOR TO enrollment. Immunostaining for the PDGFR α -positive cohort will be performed in a CLIA-certified setting. In this case, for consistency, all previously collected samples from the PDGFR α -unselected patient cohort will also undergo staining and analysis in the CLIA-certified setting.

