- E. If baseline history and physical exam is performed on a day other than C1D1, a brief visit to determine neurologic stability on current dose of steroids is also required on day 1 or day before.
- F. Only patients in the safety lead-in cohort.
- G. For women capable of pregnancy: pregnancy test at baseline; subsequently, review pregnancy risks and offer pregnancy test
- H. First “on-treatment” ECG is done approximately C1D8-C1D15 to evaluate acute changes relative to the study drug combination; the second is done approximately C3D1 to evaluate changes after a more chronic dosing of study drug combination.
- I. MRI or contrast-enhanced CT within 3 weeks prior to enrollment. An MRI is the preferred modality in all patients without a contraindication to MRI. Baseline and follow-up scans must be performed using the same modality.
- J. Imaging to be done to assess response every 2 months from initiation of treatment until off-study due to patient withdrawal, progression, or death. If MRI or contrast-enhanced CT shows response then repeat after 1 month to confirm response and then follow every 2 months from time of confirmatory MRI or CT. Patients with symptoms suggestive of progression may have imaging done between regularly scheduled scans, any time there is clinical concern for progressive disease. See also Section [10.4](#).
- K. See Section [7.8](#): After stopping study treatment, capture initiation of new therapy, first new progression date, and/or survival status since last observation approximately every 2 months during extended follow-up.
- L. Obtain and analyze archived tumor tissue per Section [11](#). During enrollment of the initial PDGFR α -unselected subgroup (prior to first interim analysis), archived tumor tissue must be obtained and analyzed, but analysis does not need to be performed prior to enrollment. After the first interim analysis, if the study proceeds to include only PDGFR α -positive patients, archived specimen analysis for PDGFR α will be required, and results must be known, prior to enrollment.
- M. Sodium, potassium, carbonate, chloride, glucose, calcium, BUN, creatinine.
- N. Additional assessments may be done at investigator discretion in patients with congestive heart failure, bradyarrhythmias, those on drugs known to prolong the QT interval, including Class Ia and III antiarrhythmics, and electrolyte abnormalities.
- O. ALT, AST, ALP, total bilirubin, direct bilirubin, albumin, total protein.

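### The rule for opening the PDGFRα design is incomplete, its power after an interim switch is below the stated 80%, and the 32–66 range counts patients differently from the 44

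*Combined protocol and SAP*

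**What the plan says.** **Design and power.** Section 13.2 sets a null rate of 20% and a target of 40% for 6-month PFS: "With a one-sided type I error of 5% and power of at least 80%, the first stage will enroll 16 response-evaluable patients". Three or fewer successes in 16 end the unselected cohort. Otherwise 17 more patients are enrolled, and 11 or more of 33 meets the efficacy criteria. The PDGFRα-positive design takes over these settings: "Both of these Simon's designs will share the same parameters/settings, assumptions for sample size, and power calculations". The same section lets positives from the first interim count toward the 16 patients of PDGFRα stage 1.

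**When the second design opens.**
- Section 1.9 speaks of an interim analysis "at which point the decision will be made whether or not to continue with all subtypes of high-grade glioma". This places the decision at 16 patients.
- Section 11.2, under "After the first interim analysis for 6-month PFS", offers two branches: continue unselected only, or continue with positives only.
- Section 4.1.1 ("After first interim analysis, if the study proceeds to enrollment of selected patients") and Study Calendar note L ("After the first interim analysis, if the study proceeds to include only") fit that reading, but they do not exclude a later switch.
- Section 3.1 says "If efficacy endpoints are not reached, the trial focus will be narrowed to include only the subgroup of patients" directly after mentioning an interim efficacy analysis, so it too reads as the first interim.
- Section 13.1 gives no time point: "If efficacy criteria are not met in patients inclusive of all molecular subtypes, then only patients with tumors that express" and so on.

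**Size.** Sections 13.1 and 13.2 give an expected total of 44 and a range of 32 to 66. The safety boundary in 13.6.2 also runs to 66.

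**The concern.** Three statements do not fit together.

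1. If only the interim at 16 opens the PDGFRα design, the total cannot exceed 16 + 33 = 49. A total of 66 needs 33 unselected patients followed by 33 positives, so failure at 33 must also open it. No section says what happens after 4 or more of 16 and then 10 or fewer of 33.
2. Positives carried over from a cohort that has just failed are not a fresh sample. Their success rate is depressed by the selection, so the second design cannot have the stand-alone power on that path.
3. The expected total and the range use different counting rules.

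At stake is a decision that would otherwise be made with outcomes already known. A negative PDGFRα result could also be read as coming from a test with at least 80% power when it had less.

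**Working it through.** **Inputs.** From 13.2: p0 = 0.20, p1 = 0.40, boundaries 3/16 and 10/33, prevalence p = 30–40%, and reuse of first-interim positives. Assumed: the rate in negatives, which the documents do not give; 0%, 10%, 20% and 40% are shown.

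**The plan's own figure.** Success probability = Σ(x = 4 to 16) P(X1 = x) · P(X2 ≥ 11 − x), with X1 ~ Bin(16, π) and X2 ~ Bin(17, π).
- π = 0.20: 0.0475
- π = 0.40: 0.8109

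Both meet the stated targets.

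**Two designs in sequence.** Enumerate exactly over the number k of positives among the first 16, the successes s among those positives, and the successes among negatives. If the total is 3 or fewer, the PDGFRα design starts with k patients and s successes. Its success probability is then Σ(a) P(A = a) · 1[s + a ≥ 4] · P(X2 ≥ 11 − s − a), with A ~ Bin(16 − k, π₊).

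Results with positives at 40%; each cell gives prevalence 30%, then 40%:

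| Rate in negatives (assumed) | Chance of interim switch | PDGFRα power given that switch | Chance of failing at 33 | Success in either cohort, interim-only | Same, failure at 33 also opens (all positives reused) |
|---|---|---|---|---|---|
| 0% | 88%, 75% | 79%, 77% | 12%, 24% | 70%, 59% | 81%, 81% |
| 10% | 64%, 52% | 76%, 73% | 33%, 40% | 52%, 46% | 81%, 81% |
| 20% | 37%, 30% | 73%, 69% | 42%, 41% | 48%, 50% | 83%, 83% |
| 40% | 6.5%, 6.5% | 67%, 61% | 12%, 12% | 85%, 85% | 94%, 93% |

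The mechanism shows in the reused positives. With negatives at 20%, their expected success rate given the failed stage is 23–25%, not 40%. If only the first 16 patients' positives are reused after failure at 33, the last column reaches 84% for negatives at 20%.

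**All patients at 20%.**
- PDGFRα test given an interim switch: false-positive rate 2.7–3.2%.
- Any false efficacy claim, interim-only: 6.4–6.7%.
- Any false efficacy claim if failure at 33 also opens the design: 8.5–8.8% (all positives reused) or 9.0–9.1% (first 16 patients' positives only).

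**Totals.**
- Full interim-switch path with reuse: 16 + 33 − 16p = 44.2 at 30% and 42.6 at 40%. This reproduces 44; without reuse it is 49.
- Two stage-1 failures: 16 + 16 = 32 without reuse. With reuse the total is 32 − k, expected 32 − 16p = 27.2 to 25.6. A total of 32 needs no positive among 16, probability (1 − p)^16 = 0.33% to 0.03%.
- Failure at 33, then both PDGFRα stages: 33 + 33 = 66 without reuse. Expected 66 − 16p = 61.2 to 59.6 if only the first 16 patients' positives are reused, or 66 − 33p = 56.1 to 52.8 if all are.

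Like the plan's 44, these totals use the unconditional expectation of k.

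**The case against.** The strongest reply is that this is mostly under-specification. Only 1.9 and the two branches in 11.2 truly fix the switch at 16. A reader might infer that 4.1.1 and the calendar note do so too, but failure at 33 also comes after the first interim, so they leave a later switch open. Section 13.1 is silent on timing rather than contrary. That stands. What remains is 1.9 and 11.2 against the figure 66, plus an outcome that no section covers.

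The reply also limits several stronger readings.
- **That the subgroup would never be tested under an interim-only rule.** Sections 2.2.1, 3.3.1 and 13.4 still estimate PDGFRα 6-month PFS with a confidence interval. It would lose its Simon decision rule, not its analysis.
- **That the chance of success in either cohort is 46–52% in general.** That holds for negatives at 10–20%. At 0% it is 59–70%, and at 40% it is 85%.
- **That PDGFRα power falls to 61–67%.** That needs negatives at 40%, where the interim switch occurs in only 6.5% of trials.
- **That the subgroup claim is inflated.** After an interim switch it is conservative, and the plan nowhere claims 5% overall.
- **That 4 years is unattainable.** Section 13.2 already expects slower PDGFRα accrual and plans more sites.

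It can also be said that 13.2 describes shared settings, not power conditional on a failed cohort. But the second design exists only under that condition, so a reader will take the stated power as applying to it.

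**Conclusion.** The point holds in three parts.

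1. **Switch rule.** The consequence of failing at 33 is undefined, and the maximum of 66 implies a route that 1.9 and 11.2 do not provide. With positives at 40% and negatives assumed at 10–20%, that outcome occurs in 33–42% of trials. Success in either cohort is then 46–52% or about 81–84%, depending on the reading and on which positives are reused.
2. **Power.** Given an interim switch, PDGFRα power is 77–79%, 73–76% or 69–73% for negatives at 0%, 10% or 20%. It is below 80% at every rate tried, against 81.1% stand-alone. The size of the shortfall rests on the assumed rate in negatives; the direction did not change over 0–40%.
3. **Sizes.** 44 counts reuse, while 32 and 66 do not. With reuse, 32 is not a minimum; if the switch is interim-only, 66 cannot be reached.

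The stand-alone boundaries are correct. The 30–40% prevalence is quoted for GBM and may differ in this grade 3–4 population.

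**What to change.** Leave the boundaries unchanged.

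(a) State whether failure at 33 opens the PDGFRα design and, if so, which positives are reused. Bring 1.9, 3.1, 4.1.1, 11.2, calendar note L, 13.1, 13.2 and 13.6.2 into line.

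(b) Replace the shared-power sentence in 13.2 with: same boundaries; stand-alone alpha 4.75% and power 81.1%. For the chosen rule, add the PDGFRα power given a switch over a stated range of rates in negatives, the chance of each path, and the chance of any false efficacy claim with all patients at 20%.

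(c) Recompute the sample-size range with the same reuse as the 44, giving expected totals separately from limits. If the switch is interim-only, the maximum is 49.

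As a minor clarification, restate the 4-year estimate with the 30–40% prevalence and the added sites, and reconcile those sites with the single-center description in 3.1.

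The cost is recalculation and wording, with no change to the boundaries. The stated power becomes slightly less favourable.
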